#### 6 TREATMENTS AND MEDICATIONS

# 6.1 Prior Anti-Cancer and Radiation Therapy

Prior anti-cancer therapies will be coded per World Health Organization drug dictionary (WHO-DD).

The following will be summarized categorically or with descriptive statistics as appropriate for all subjects in the ITT and Safety population:

- Received prior sorafenib for HCC (Yes, No)
- Descriptive summary for duration of treatment in months on prior sorafenib for HCC
- Categorical summaries for duration of treatment in months on prior Sorafenib for HCC as follows:
  - $\circ$  < 1 month,  $\geq$  1 month
  - $\circ$  < median,  $\geq$  median
- Number and percent of subjects who progressed on the most recent prior systemic non-radiation anti-cancer therapy for HCC (Yes, No)
- Number and percent of subjects who got prior sorafenib as the most recent prior anticancer therapy for HCC and progressed (Yes, No)
- Cross tabulation of type of non-radiation therapy (Local, Systemic and Unknown) with indication (for HCC [Local-Liver directed, Local-Other locations, Adjuvant, Advanced, Other], Other than HCC)
- Number of prior systemic non-radiation anti-cancer regimens for advanced HCC per subject  $(1, 2, \ge 3)$  and descriptive statistics

- Number of prior systemic non-radiation anti-cancer agents for advanced HCC per subject  $(1, 2, \ge 3)$  and descriptive statistics
- The time from the end of most-recent non-radiation prior systemic anti-cancer treatment for HCC to randomization will be summarized descriptively Number of prior radiation therapies for HCC per subject  $(1, 2, \ge 3)$  and descriptive statistics
- Subject incidence of radiation therapy by indication from history of radiation therapy (Disease under study and Other)
- Subject incidence of radiation therapy type (External beam radiation therapy
  [EBRT], Internal radiation therapy [brachytherapy], Radioisotope therapy,
  Radioembolization, Radiofrequency ablation and Other) from history of radiation
  therapy received for HCC or Other indications
- Subject incidence of site (Bone, Soft-tissue, Systemic, Unknown) of radiation from history of radiation therapy received for HCC or Other indications

All prior non-radiation anti-cancer agents will be summarized categorically by Anatomical Therapeutic Chemical (ATC) Class Text and WHO-DD base substance preferred name by treatment arm and type of therapy (Local-liver directed, Local-non-liver directed, Systemic, Unknown) for all subjects in the ITT population.

#### 6.2 Prior and Concomitant Medications

Medications recorded on the CRFs will be coded using the WHO-DD. Prior and concomitant medications, other than prior and subsequent anticancer therapies will be summarized by treatment group in the Safety population by ATC and WHO-DD base substance preferred name. In addition, prior medication will also be summarized in the ITT population by ATC and WHO-DD base substance preferred name. Anticancer therapies are addressed in sections 6.6 and 6.7 of this plan.

### 6.3 Study Treatment Exposure

Study treatment exposure will be summarized with descriptive statistics in the Safety population.

The following will be derived for each subject and will be summarized:

 Duration (in months) of exposure per subject, calculated as (date of decision to discontinue study treatment – date of first dose + 1) /30.4375

- Average daily dose per subject (mg/day) of cabozantinib (or cabozantinib-matched placebo), calculated as (total dose received / duration of exposure)
- Percent dose intensity for cabozantinib (or cabozantinib-matched placebo) calculated as 100\*(average daily dose mg/day) / (60 mg/day)
- Duration of treatment in months defined as (date of decision to discontinue study treatment date of first dose total duration of dose holds + 1) /30.4375

### **6.4** Study Treatment Modifications

Treatment modifications (holds and reductions) for cabozantinib (or cabozantinib-matched placebo) will be summarized in the Safety population. Only modifications due to AE will be summarized.

- A. The following summaries will be presented for the cabozantinib (or matched placebo) component of study treatment:
  - i. For dose reductions due to AE

#### Categorical summaries for:

- Subjects with any dose reduction
- Dose levels received by a subject
- Lowest non-zero dose level received
- Last non-zero dose level received
- Last dose level received (including dose holds)

### Descriptive statistics for:

- Duration of treatment in months for each dose level (60 mg, 40 mg, 20 mg, 0 mg)
- Time to first dose level reduction (first receipt of 40mg) (days)
- Time to second dose level reduction (first receipt of 20mg) (days)
- ii. Summaries for dose holds due to AE:
  - Descriptive statistics for number of dose holds due to an AE
  - Descriptive statistics for duration of dose holds per dose hold and per subject due to an AE, calculated as (stop date of hold start date of hold + 1)
  - Categorical summary for subjects with duration of holds due to an AE that can be classified as any number of days,  $\geq 7$  days,  $\geq 14$  days, and  $\geq 21$  days

- Descriptive statistics for time to first dose hold, time to first dose hold that
  was ≥ 7 days, ≥ 14 days, and ≥ 21 days. The time to dose hold is calculated
  as (start date of the hold first dose date + 1)
- Descriptive statistics for time to second dose hold, time to second dose hold that was  $\geq 7$  days,  $\geq 14$  days, and  $\geq 21$  days
- iii. Summaries for dose modifications (defined as a reduction or hold) due to AE:
  - Frequency counts and percentages for subjects with any dose modifications
  - Descriptive statistics for number of dose modifications (0-3)
  - Descriptive statistics for time to the first dose modification
  - Descriptive statistics for time to the second dose modification

# 6.5 Study Treatment Non-Compliance and Dosing Errors

Treatment non-compliance and dosing errors for reasons other than AE will be summarized in the Safety population. Frequency counts and percentages will be presented by treatment groups for:

- Subjects with dose hold (0 mg) due to non-compliance
- Subjects who received dose > maximum allowed dose level at any time
- Subjects who received wrong dose (≤ maximum allowed dose level) at any time due to non-compliance
- Subjects who received wrong dose (≤ maximum allowed dose level) at any time due to site/logistic error or other reason

# 6.6 Non-Protocol Anti-cancer Therapy

For the purpose of supporting safety evaluation:

Non-radiation concomitant (see definition in section 4.6.) NPACT will be summarized by ATC text and WHO Drug base substance preferred name in the Safety population.

For the purpose of supporting efficacy evaluation:

All subsequent (see definition in section 4.6.) NPACT, including radiation therapy, will be summarized by treatment group in the ITT population as follows:

- Based on the non-radiation therapy received subjects will be categorized into one or more of the following categories: systemic, local, or unknown and all NPACTs falling under these categories will be summarized by ATC text and WHO Drug based substance preferred name
- Time to first systemic NPACT will be summarized by descriptive statistics
- Frequency counts and percentages will be presented for radiation therapy indication, type and site

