#### **1.4.3 Rationale for Cabozantinib Dose Selection**

Data from a Phase 2 randomized discontinuation trial (XL184-203) of cabozantinib showed activity in multiple solid tumors including HCC and employed a dose of 100 mg daily, orally. This study enrolled a cohort of 41 subjects with advanced HCC. Subjects were required to have Child-Pugh class A scores at study entry. In this cohort encouraging anti-tumor activity was observed with 78% of subjects experiencing measurable disease regression in their target lesions

as their best response, a median PFS of 5.2 months, and a median OS of 11.5 months. The Week 12 disease control rate (PR or stable disease) was 66%. Fifty-nine percent of the HCC subjects required at least one dose reduction, resulting in a median average dose of approximately 66 mg/day. The median time to first dose reduction to 60 mg was 39.5 days. Subjects maintained disease control despite dose reductions as evidenced by the high rate of Week 12 disease control.

Additionally, the 60 mg cabozantinib daily dose has been evaluated in two Phase 3 studies in metastatic castration-resistant prostate cancer. The choice of dose for these studies is supported by data from a Phase 1 and a Phase 2 study employing a 40 mg dose of cabozantinib (Smith 2012, DeBono 2012); these studies showed improved tolerability compared to results from a cohort of subjects receiving the 100 mg dose of cabozantinib while maintaining anti-tumor activity. Therefore, a dose of 60 mg cabozantinib daily is expected to show antitumor activity. If dose reductions are necessary, it is also expected that antitumor activity can be maintained at the lower doses.

Finally, the 60 mg cabozantinib daily dose has demonstrated efficacy and safety in a Phase 3 study in advanced renal cell cancer (RCC; Choueiri et al 2016, Choueiri et al 2015) leading to US approval of cabozantinib tablets in patients with advanced RCC who have received prior anti-angiogenic therapy.

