### 4 GENERAL CONVENTIONS

The statistical principles applied in the design and planned analyses of this study are consistent with International Conference on Harmonization (ICH) E9 guidelines (ICH 1998).

Continuous data will be summarized using descriptive statistics (number of observations, mean, standard deviation, median, 25th and 75th percentiles, minimum, and maximum). Frequencies and percentages will be used for summarizing categorical (discrete) data.

Confidence intervals, when presented, will generally be constructed at the 95% level. For binomial variables, the normal approximation methods will be employed unless otherwise specified.

A month is operationally defined to be 30.4375 days. Six months is operationally defined to be 183 days.

All summaries will be presented by treatment arm unless otherwise specified.

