# 4.4 Missing and Partial Data

In general, other than for partial dates, missing data will not be imputed and will be treated as missing. The algorithms for imputation of partial dates vary depending upon the parameter. These are presented in Appendix A.

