# 7.5.3 Time to Objective Response

Time to objective response is defined as the time from randomization to the first documentation of objective response by the investigator that is subsequently confirmed at a visit that is  $\geq 28$  days later to disease progression or death due to any cause.

Time to objective response (months) = (date of first objective response - date of randomization + 1)/30.4375

Time to objective response will be computed only among subjects who experience an objective response (confirmed CR or confirmed PR), and arithmetic methods (not Kaplan-Meier) will be used.

The analyses for time to response will be performed only if ORR >10%.

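### Time to first systemic non-protocol therapy is summarized only among recipients, so its between-arm comparison depends on survival and data cutoff as well as on how soon therapy starts

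*SAP*

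**What the plan says.** SAP 6.6 divides its NPACT summaries into a safety part and a part headed "For the purpose of supporting efficacy evaluation". In the second part, for the ITT population, it says "Time to first systemic NPACT will be summarized by descriptive statistics". It names no time origin, no censoring rule and no Kaplan-Meier method.

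Two general rules fill the gap. SAP 4 says "Continuous data will be summarized using descriptive statistics (number of observations, mean, standard deviation, median", followed by quartiles and range. SAP 4.4 says "In general, other than for partial dates, missing data will not be imputed and will be treated as missing". A subject who dies, is lost or reaches the cutoff without NPACT has no time value and so does not enter the summary. This restriction is implied by the rules, not written in 6.6.

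SAP 6.4 treats times to first and second dose reduction, hold and modification due to adverse events in the same way, in the Safety population.

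Elsewhere the SAP is explicit. OS, PFS and duration of response have censoring rules and Kaplan-Meier estimates. For time to response, 7.5.3 restricts the analysis to responders and says "arithmetic methods (not Kaplan-Meier) will be used".

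**The concern.** Time to first NPACT is a time-to-event quantity: death competes with it and the cutoff censors it. Its mean among recipients reflects how fast subjects leave follow-up by any route, so it does not isolate how soon NPACT begins. In the arm with longer survival, more late starts are observed and the mean rises, even if the rate of starting NPACT is identical.

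The design assumes longer survival on cabozantinib, so the plan's own assumptions predict this pattern. Because the row is offered in support of efficacy, a longer time on cabozantinib could be taken as a delayed need for further therapy. NPACT also triggers censoring in the primary PFS analysis (SAP 7.2.1.1) and in the exploratory OS analysis (SAP 7.1.4), so readers of those results have reason to look at its timing by arm.

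**Working it through.** **Inputs from the documents.** SAP 2.4 gives median OS of 8.2 months (placebo) and 10.8 months (cabozantinib), exponential survival, HR 0.76, allocation 507 and 253, 25 months of accrual, and about 38 months to 621 deaths.

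**Assumed.** The NPACT hazard h is 0.02, 0.05 or 0.10 per month, the same in both arms, constant from randomization and independent of death. Entry is uniform.

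**Plan's own figures.** 8.2 / 0.76 = 10.8 months, as stated. Expected deaths at 38 months are 615 with 25 months of accrual, or 621 at 31.5 subjects per month, so the stated 621 is reproduced. The 311 deaths for the first interim fall at about 21 months.

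**Death hazards.** ln 2 / 8.2 = 0.0845 per month (placebo); ln 2 / 10.8 = 0.0642 per month (cabozantinib).

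**Formula.** Let d be the death hazard and G(t) the chance that follow-up to the cutoff exceeds t. At 38 months, G(t) = 1 up to month 13 (38 - 25) and (38 - t)/25 after that. At 21 months, G(t) = (21 - t)/21. Then

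mean among recipients = ∫ t e^(-(h+d)t) G(t) dt / ∫ e^(-(h+d)t) G(t) dt.

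| h per month | Cutoff (months) | Placebo mean (months) | Cabozantinib mean (months) | Gap (months) | Gap (%) |
|---|---|---|---|---|---|
| 0.02 | 38 | 7.5 | 8.4 | 0.9 | 12 |
| 0.05 | 38 | 6.4 | 7.1 | 0.7 | 11 |
| 0.10 | 38 | 5.1 | 5.5 | 0.5 | 10 |
| 0.02 | 21 | 4.8 | 5.2 | 0.4 | 7 |
| 0.05 | 21 | 4.4 | 4.7 | 0.3 | 7 |
| 0.10 | 21 | 3.7 | 4.0 | 0.2 | 7 |

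Gaps are taken before rounding. The cutoff alone moves the value: at h = 0.05 the cabozantinib mean is 4.7 months at the 21-month cutoff and 7.1 at the 38-month cutoff.

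**Equal survival.** With median OS 8.2 months in both arms and a true median time to NPACT of 12 months, simulation gives 6.16 against 6.16 months. The gap comes from the survival difference.

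**NPACT only after study treatment.** Simulation with a mean of 4 months on treatment in both arms (assumed), followed by NPACT at a rate with median 3, 6 or 12 months, gives placebo and cabozantinib means of 6.01 and 6.36, 7.45 and 7.99, and 8.70 and 9.43 months. The gaps are 0.35, 0.54 and 0.73 months (6%, 7% and 8%).

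**What the alternatives show at h = 0.05, month 12.**
- Censoring at death: 1 - e^(-0.05 × 12) = 45% in both arms, cause-specific hazard ratio 1.0.
- Cumulative incidence with death competing, h/(h+d) × (1 - e^(-12(h+d))): placebo 0.372 × 0.801 = 30%; cabozantinib 0.438 × 0.746 = 33%.

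Cumulative incidence alone therefore also differs between arms at equal NPACT rates.

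**The case against.** **The row is minor and the question is covered elsewhere.** It is one untested descriptive line, and SAP 7.3 calls efficacy evaluations other than OS, PFS and ORR exploratory. PFS2 in SAP 7.2.1.4 counts NPACT as an event, and SAP 7.1.4 reanalyses OS with censoring at systemic NPACT or liver-directed therapy. The low importance stands. The substitution does not: PFS2 mixes NPACT with progression, death and other events, and the OS reanalysis estimates survival. Neither estimates time to NPACT.

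**The denominators are visible.** Descriptive statistics include the number of observations, and SAP 6.4 tabulates subjects with any reduction. This lets a careful reader see the restriction, but it does not remove the dependence on survival.

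**A constant NPACT rate from randomization is unrealistic.** Protocol 7.1.2 does not permit systemic anticancer therapy during study treatment, so NPACT timing partly follows time on treatment, and a longer time on cabozantinib could be a genuine delay. This stands as a caution. With NPACT starting only after treatment stops, the gap is smaller but still present.

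**Stronger readings a reader might infer.**
- That the arms would differ when nothing differs. They would not: with equal survival the means agree.
- That the gap is 12-24%, from 1/(h+d) with unlimited follow-up (9.6 vs 11.9, 7.4 vs 8.8 and 5.4 vs 6.1 months). SAP 2.4 plans a cutoff near 38 months, which about halves the upper end.
- That dose-reduction times are distorted between arms. This needs unequal time on treatment; Protocol 3.2 gives only an overall average of 3 to 5 months.
- That the statement "The median time to first dose reduction to 60 mg was 39.5 days" in Protocol 1.4.3, with its 59% reduced, shows the distortion. It comes from another study with a 100 mg starting dose, and the protocol does not say whether that median was taken among reducers only.

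**Conclusion.** The concern holds for time to first systemic NPACT. Followed as written, SAP 6.6 gives a value among recipients that depends on survival and cutoff. Under the planned survival medians and an identical NPACT rate of 0.02 to 0.10 per month, it favours cabozantinib by about 10-12% (0.5-0.9 months) at 38 months and about 7% at a 21-month cutoff. These sizes rest on assumed constant NPACT rates, independence of NPACT and death, and the planned OS difference being real.

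For dose reductions and holds in SAP 6.4, the same restriction to subjects with the event applies. The documents do not support a size for any between-arm effect there.

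This is a minor reporting improvement. OS, PFS, ORR, alpha and sample size are untouched.

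**What to change.** In SAP 6.6, define time to first systemic NPACT from randomization in the ITT population, with subjects without NPACT censored at death, last contact or data cutoff. Report Kaplan-Meier curves or a cause-specific hazard ratio by arm. Beside this, show cumulative incidence with death as a competing event, at fixed times that include 6 and 12 months. Both are needed: the first compares rates of starting NPACT but relies on independence from death, and the second gives the share who actually received it but moves with survival. Label any plain summary 'among subjects who received NPACT'.

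In SAP 6.4, label the times to reduction, hold and modification 'among subjects with the event'. Cumulative incidence there is optional.

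The cost is SAP wording and one or two extra tables or curves. NPACT and death dates are already collected (Protocol 5.5.2), and SAP 4.8 allows a revised plan or an addendum before unblinding.

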# 6.7 Post-randomization Surgery/Procedure

Post-randomization surgery/procedures that impacted the tumor lesion(s) (Yes, No, Unknown) will be summarized by treatment group for subjects in the ITT and Safety populations.

#### 6.8 Concomitant Transfusions

Concomitant transfusions will be summarized by transfusion type and treatment group for subjects in the safety population.

#### 7 EFFICACY ANALYSES

Primary efficacy analyses will be performed on all subjects in the ITT population.

# 7.1 Primary Efficacy Endpoint (OS)

### 7.1.1 Definition

The primary efficacy endpoint is overall survival. Duration of OS is defined as the time from randomization to death due to any cause. For subjects who are alive at the time of data cutoff but are permanently lost to follow-up, duration of OS will be right censored at the date the subject was last known to be alive. Those who withdraw consent from survival follow-up and are alive will be right censored at the date the subject withdrew consent from survival follow-up. Subjects alive on or after the data cutoff or those who died after the data cutoff will be right censored at the date of data cutoff.

OS (months) = (earliest date of death or censoring – date of randomization + 1)/30.4375

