Clinic visits for safety evaluations will occur prior to dosing on W1D1 and at minimum every 2 weeks ( $\pm$  3 days) after treatment is initiated through W9D1 and then every 4 weeks ( $\pm$  5 days) thereafter independent of any dose interruptions. The final safety assessment will occur at the post-treatment follow-up visit 30 (+14 days after the date of the decision to discontinue treatment) unless a Grade 3/4 AE or an SAE is determined to be ongoing (see Section 8.3.4).

If study treatment is interrupted, investigators should perform additional safety assessments weekly or more frequently as clinically indicated. Results of safety assessments should be reviewed as soon as they become available in order to make timely decisions regarding the continuation, interruption, or restarting of study treatment.

Radiographic tumor assessments (Section 5.7.6) and HRQOL assessments (Section 5.7.8) should be performed according to the schedule in Appendix A (Appendix B for the Open-Label Phase, Appendix C for the Maintenance Phase [HRQOL will not be assessed in the Open-Label Phase or Maintenance Phase]).

In accordance with the ITT principle, HRQOL, and radiographic tumor assessments, as well as survival follow-up, are to be performed per protocol even for subjects randomized but who never receive study treatment. For such subjects, W1D1 is defined as the date of randomization.

Child-Pugh Score every 8 weeks ( $\pm$  5 d) after randomization (W9D1, W17D1 etc). Child-Pugh assessments should continue regardless of whether study treatment is given, reduced, interrupted, or discontinued until the later of 8 weeks after radiographic progression per RECIST 1.1 as determined by the investigator or the date of the decision to permanently discontinue study treatment. (Please see Appendix B for the Open-Label Phase, Child-Pugh assessments will be discontinued for the Maintenance Phase).

Blood samples for pharmacogenetic, plasma biomarker, serum bone marker analyses, and potential CTC analysis (Section 5.7.11) will be collected according to the schedule in Appendix A. (These assessments will be discontinued for the Open-Label Phase or Maintenance Phase.)

In addition, tumor tissue (archival or recently biopsied) will be obtained (Section 5.7.11) at enrollment whenever available for exploratory analysis of MET and potentially other pathway components or modulators associated with the mechanism of action of cabozantinib as predictive biomarkers.

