### **5.5.2 Extended Follow-up**

Following treatment discontinuation for whatever reason, subjects will continue to be followed either via clinic visit or telephone contact approximately every 8 weeks for the following information unless the subject withdraws consent from all aspects of the study:

- Survival status of subject or date of death and primary cause of death

- Receipt of subsequent anticancer therapies (drug or procedure name and dates)

Radiographic disease assessments, EQ-5D-5L, and Child-Pugh assessments are to continue in the Extended Follow-Up period as necessary per the schedule for these assessments in Appendix A.

Subjects will be followed until death or until the Sponsor's decision to no longer collect these data.

At each contact, the investigator (or designee) will determine if the subject died, and if so, record the date and cause of death. All efforts must be undertaken by the study sites to determine the date of death (or date subject last known alive at the time of a data cut-off). This may include, but not necessarily be limited to telephone contacts, communication at study visits, registered letters, and reviews of local obituaries and government death records. If subject is lost to follow-up, multiple attempts to contact must be made and documented in the subject records.

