#### **9.2.1 Definition**

Duration of OS is defined as the time from the randomization to the death due to any cause. For subjects who are alive at the time of data cutoff or are permanently lost to follow-up, duration of OS will be right censored at the date the subject was last known to be alive.

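### SAP 7.1.1 and Protocol 9.2.1 give different OS censoring rules for subjects still in follow-up who were last contacted before the data cutoff

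*SAP*

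**What the plan says.** Protocol 9.2.1 has one censoring rule for OS. It opens "For subjects who are alive at the time of data cutoff or are permanently lost to follow-up" and sends both groups to the date last known alive.

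SAP 7.1.1 has three rules:

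1. Date last known alive, "For subjects who are alive at the time of data cutoff but are permanently lost to follow-up".
2. Date of withdrawal, for living subjects who withdraw consent to survival follow-up.
3. Date of cutoff, in a sentence that reads, up to its last word: "Subjects alive on or after the data cutoff or those who died after the data cutoff will be right censored at the date of data".

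After treatment ends, Protocol 5.5.2 has subjects followed "either via clinic visit or telephone contact approximately every 8 weeks". On treatment, Protocol 5.2 has visits every 2 weeks "through W9D1 and then every 4 weeks".

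Protocol 5.5.2 also tells sites to make every effort to establish, as of a data cutoff, the date of death or the last date known alive, using calls, letters, obituaries and death records. SAP Appendix A (incomplete death dates) shows that the last-known-alive date is collected on the survival follow-up form.

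**The concern.** The SAP has *but* where the protocol has *or*. That word takes living subjects who are still being followed out of the last-known-alive rule. With contacts about 8 weeks apart, a last contact before the cutoff is the usual state of a living post-treatment subject unless someone makes a special check.

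If such subjects are carried to the cutoff while deaths since their last contact are still unreported, they add time at risk without the matching events. Kaplan-Meier medians and landmark survival are then too high. The effect is largest at the first interim, when most of the follow-up is recent, and that is an analysis at which the trial may stop and report.

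SAP Table 2 does not list or explain the difference, although SAP 4.8 says substantive departures from the protocol's analyses will be documented.

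**Working it through.** **Which rule applies.** Take a subject not known to have died, not withdrawn, not lost, and last contacted 5 weeks before the cutoff.

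- Protocol 9.2.1: censored at last contact.
- SAP rule 1 does not apply (not lost). Rule 2 does not apply (not withdrawn).
- SAP rule 3 depends on the meaning of *alive*. If it means not known dead, the subject is censored at the cutoff and gains 5 unobserved weeks. If it means confirmed alive on or after the cutoff, no rule applies.

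Rule 1 calls even permanently lost subjects alive at the cutoff, which favours the first meaning. The phrase *on or after* in rule 3 favours the second. The text does not settle it.

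**The plan's own figures.** Inputs (SAP 2.4): HR 0.76, 2:1 allocation, two-sided 5%, 90% power, placebo median 8.2 months, exponential survival.

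- Deaths = (1.960 + 1.282)² / [(2/3)(1/3)(ln 0.76)²] = 10.51 / (0.2222 × 0.0753) = 628. With HR = 8.2/10.8 it is 624. The plan has 621.
- Lan-DeMets O'Brien-Fleming boundaries come out at p = 0.0031, 0.0184 and 0.0440. The plan has 0.0031, 0.0183 and 0.044.
- At 31.5 subjects per month, 621 deaths fall at 38.0 months. The plan has about 38.

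The design is reproduced, and the censoring rule does not alter the number of deaths it needs.

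**Worst case for rule 3 under the first meaning.** Assumptions, since the documents give no distribution of contact lag:

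- Last contact is uniform over 0 to 8 weeks before the cutoff in both arms (8 weeks = 56/30.4375 = 1.84 months; mean 0.92).
- Deaths after last contact are unknown.
- Data are extracted at the cutoff.
- The cutoff is set at the 311th, 466th or 621st actual death.

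There were 1,500 simulated trials per row. Medians are in months, cabozantinib/placebo.

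| Deaths | Full information | Last-known-alive rule | Cutoff rule | HR, last-known-alive vs cutoff |
|---|---|---|---|---|
| 311 | 10.79 / 8.24 | 10.83 / 8.27 | 11.60 / 8.79 | 0.760 vs 0.761 |
| 466 | 10.84 / 8.24 | 10.85 / 8.25 | 11.27 / 8.53 | 0.758 vs 0.759 |
| 621 | 10.79 / 8.22 | 10.79 / 8.22 | 10.79 / 8.22 | 0.761 vs 0.762 |

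- First interim: 11.60 − 10.79 = 0.81 and 8.79 − 8.24 = 0.55 month too long. A separate simulation of 400,000 subjects gave 11.5 and 8.7 against 10.8 and 8.2, that is 0.7 and 0.5.
- Second interim: 0.43 and 0.29. Final: none.
- Time credited at the first interim: 4,415 − 4,098 = 317 person-months, or 317/4,415 = 7.2%. As a rough check, about 335 living subjects × 0.92 = 308.
- Deaths not yet known at the first interim: 311 − 288.6 = 22.4, also 7.2%.

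**A milder case.** Suppose data are extracted 4 weeks after the cutoff. The last 8-weekly contact is then uniform from 4 weeks before to 4 weeks after the cutoff. Half the subjects have no gap and the rest average 2 weeks, so the mean gap is 0.5 × 2 = 1 week instead of 4. With on-treatment visits also counted (assumed mean 4 months on treatment), the first-interim medians are 10.95 and 8.3 against 10.8 and 8.2, an error of about 0.1 month. With an 8-week lag the error is zero.

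**Unequal lag.** With assumed gaps of 8 weeks on placebo and 4 on cabozantinib, the cutoff rule gives HR 0.789, 0.778 and 0.763 at the three analyses, against 0.760, 0.760 and 0.757 with full information. The shift is toward no effect.

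**The case against.** The strongest reply is that rule 3 can be read as covering only subjects confirmed alive at or beyond the cutoff. For them, censoring at the cutoff is correct. A reader might infer that the SAP definitely adds unobserved survival time. The documents do not support that, because it follows from only one of two possible readings. What remains under the other reading is a missing rule on the primary endpoint, which a programmer would have to fill by choice.

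Second, Protocol 5.5.2 already asks sites to establish status as of a cutoff, and SAP Section 10 plans a data review before extraction. The half-month shifts are therefore near worst case. This stands. However, the protocol asks for effort, does not require confirmation of status on or after the cutoff, and gives no lag between cutoff and extraction.

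Third, last-known-alive censoring has a weakness of its own. Public records can reveal deaths while rarely confirming that someone is alive. If deaths are known up to the cutoff but living subjects are censored at last contact (8-week gaps), the first-interim medians are 10.18 and 7.81 against 10.79 and 8.24. They are too short by 0.61 and 0.43 month. With the unequal lag above, the HR is 0.735 against 0.760, which favours cabozantinib. This objection also stands, so the remedy has to cover ascertainment as well as wording.

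**Conclusion.** The conflict between the two documents is real and concerns the primary endpoint. For a followed subject last contacted before the cutoff, the SAP either credits unobserved time or is silent, while the protocol is explicit.

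Under the first reading, the upward error in first-interim medians runs from zero (status confirmed on or after the cutoff), through about 0.1 month (4-week extraction lag), to about 0.5 month on placebo and 0.7 to 0.8 on cabozantinib (8-week contacts, no check). For scale, the planned gain in median is 10.8 − 8.2 = 2.6 months. All these sizes rest on assumed contact and extraction lags and on the design's exponential model.

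A reader might also infer that the primary test or its type I error is at risk. The calculations do not support that. With equal lag the HR moves by no more than about 0.001, final medians do not change, and in the one unequal-lag case tested the cutoff rule was conservative. The matter is worth correcting because it affects reported interim estimates and the reproducibility of the primary analysis.

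**What to change.** In SAP 7.1.1, replace the first and last censoring sentences with: *Subjects not known to have died on or before the data cutoff are censored at the earlier of the date last known alive and the data cutoff date.* Keep the withdrawal rule, and record the change in the version history.

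Add two supports:

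- Have sites update survival status as of each cutoff, using the procedures already in Protocol 5.5.2, so that deaths and living status are known to the same date.
- Report cutoff-date censoring as a sensitivity analysis for the medians and HR. If the two rules agree, incomplete status at the cutoff has not affected the result.

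The cost is one sentence, one additional table, and site effort the protocol already asks for. The last-known-alive date is already collected, and the 621-death design is unchanged. Interim medians may come out slightly less favourable than under cutoff censoring. Without the status update, the new rule could err in the opposite direction by a similar amount.
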